Trial medication refers to dosing with atezolizumab.

Treated Subjects

A subject is considered treated once they have received the first dose of trial product.

Trial Day (Study Day)

The day of trial is defined from the day of first vaccination. The day of first vaccination is defined as Day 1, the day after first vaccination is Day 2, and so on. Similarly, the day before first vaccination in the screening period is defined as Day -1, and so on. Note, no reference is made to the time of the vaccination in the calculation of the trial day, i.e., at midnight a new trial day begins regardless of the time of first vaccination. Note, to maintain conformance with Clinical Data Interchange Standards Consortium (CDISC) data standards, in datasets “trial day” will be referred to as “study day.”

Baseline

If not otherwise specified, “baseline” refers to the last measurement prior to first treatment with vaccine, including re-screening or pre-treatment unscheduled visit values. Note for determination of baseline values, data that are collected on the day of first vaccination but prior to the first vaccination, per protocol, will be considered pre-treatment data and will be eligible to be used as baseline values. Baseline data will be summarized without specification as to which visit the data were originally reported.

In cases where no pre-treatment values exist for a baseline parameter within a subject, the subject will be considered as having no baseline, and post-baseline changes and percent changes will not be able to be calculated.

Screening Phase

All data collected from the initial screening visit (within 28 days prior to first dose) until first dose of trial vaccine. This may include any unscheduled or re-screening visit results up to the first trial vaccination.

Active Trial Phase

All data collected at the visit of first vaccination (Visit 1) through Visit 14 plus 30 days, including unscheduled visits, will be considered part of the active trial phase. For safety analyses, data will be collected until 30 days (Visit 14 for completers) after the last treatment. For subjects who discontinue treatment early, the 30 days will start at the most recently received trial product.

Long Term Follow-up (LTFU) Period

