A TEAE is an AE with an onset on or after initiation of trial product, or an AE present at initiation of trial product that worsens. This includes all AEs occurring from first dose of trial product through 30 days after of last dose of trial product, if unrelated to trial product or non-serious. All trial product-related SAEs and AESIs through 100 days after the last dose of trial product will be counted as TEAEs.

Related TEAEs

A TEAE is determined to be related to trial product for the purpose of CSR reporting if assessed by the investigator as possible, probable, or definitely related to trial product. If a relationship is missing and the TEAE started after the initiation of an individual trial product, then the TEAE will be analyzed as being related to that individual trial product. Relationship will be collected separately for MVA-BN-CV301, FPV-CV301, and atezolizumab.

Serious Adverse Events

AEs that meet the seriousness criteria as described in Section 8.1.4 of the trial protocol are considered serious adverse events (SAEs). Collection of SAEs begins at the signing of the ICF and continues for 30 days after the last treatment with trial product for unrelated events, and for 100 days after the last dose for treatment-related events.

Severe Adverse Events

AEs are graded for severity using the National Cancer Institute's Common Terminology Criteria for Adverse Events (NCI CTCAE) version 5.0. Levels include 1: Mild, 2: Moderate, 3: Severe, 4: Life Threatening, and 5: Death. For analysis, severe AEs will include AEs \geq Grade 3.

Adverse Events of Special Interest

AEs of special interest (AESIs) include Immune-mediated AEs (IMAEs) and cardiac events but may also include other events based on the opinion of the investigator. Autoimmune diseases and immune-mediated clinical syndromes, occurring after first treatment with trial

product, will be reported as potential IMAEs. In addition, cardiac events are considered AESIs. A Cardiac AESI is defined as:

- Any cardiac sign or symptom (attributed by the investigator to be cardiac related) developed since the first vaccination
- ECG abnormalities determined to be clinically significant developed since the first vaccination

Additionally, for atezolizumab AESIs will be reported based on the manufacturer's requirements (See trial protocol section 8.1.3 for further details).

1 Introduction

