4.3.2 Missing or Partial Dates

All data will be listed and summarized as captured in the electronic Case Report Form (eCRF) or transferred from external sources (e.g., lab, ECG). It may be necessary to impute incomplete dates to correctly assign events to a period or to calculate durations.

For prior and concomitant medications, AEs, and cancer history dates the following rules will apply:

Missing	Rule for start date	Rule for end date	Flag for imputation
Day	First of month	Last of month*	D
Month [†]	1 January	31 December*	M
Year [†]	First Treatment Date	Date of Data Cutoff/Lock	Y

* Unless the imputed start date is before first visit date, in which case first visit date is used; or the imputed stop date is after last visit date in which case last visit date available is used.

† It is assumed that a missing Month implies a missing Day as well, and that a missing Year implies a missing Month and Day.

If the imputation of an AE start date leads to a date prior to the date of first vaccination, and it is possible that the AE start date can be on or after date of first vaccination based on partial date information (e.g., occurred on the same month), it will be set to the date of first vaccination to be conservative. In the event the imputation of an end date leads to a date after the death date of a subject, the death date will replace the imputed date.

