4.3.4 Assignment of AEs to Treatment Period

Each AE will be assigned to a treatment period using date of vaccination (or infusion if this is the final treatment) and date of onset of AE:

- All AEs beginning before the first treatment with trial product will be classified as pre-treatment AEs belonging to the Screening Phase.
- All AEs starting on the day of first MVA-BN-CV301 vaccination until the day prior to the first FPV-CV301, or until early treatment termination, will be assigned to the MVA Vaccination Period.

- All AEs starting after the first FPV-CV301 vaccination through 30 days post-last trial product, or until early termination, will be assigned the FPV Vaccination Period.
- All AEs starting after the first dose of trial product through 30 days post last trial product (CV301 or atezolizumab, whichever is latest) will be included in the Overall Treatment Period.
- Related SAEs and AESIs starting after 30 days but prior to 100 days after the last trial product dose will be assigned to the FU phase of the trial. Other AEs (i.e., not serious or unrelated) occurring during the same time period will be assigned to the FU phase but excluded from tables, if collected, as they are not considered treatment emergent.

If an AE coincides with the date of a vaccination, the AE will be assigned to the treatment period corresponding to the vaccination on this date to be conservative.

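### SAP 4.3.2 imputes AE start dates without checking a known end date, so an AE that resolved before the first dose can be counted as treatment-emergent

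*SAP*

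**What the plan says.** SAP 4.3.2 states that incomplete dates may be imputed to place events in the right period and to compute durations. For AE start dates its table gives three rules:

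- missing day: "First of month";
- missing month: 1 January;
- missing year, which the SAP takes to mean the whole date is missing: "First Treatment Date".

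One correction follows the table. It is triggered "If the imputation of an AE start date leads to a date prior to the date of first vaccination". It also requires that "it is possible that the AE start date can be on or after date of first vaccination based on partial date information", and the SAP's example is onset in the same month. The result is that "it will be set to the date of first vaccination to be conservative". Under General Definitions (Trial Day), "The day of first vaccination is defined as Day 1". The section compares an imputed end date with the date of death, but never compares an imputed start with a known end.

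Three other parts of the SAP matter here:

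- **AE collection** begins at consent (General Definitions, Adverse Event). SAP 4.4.7.6 and 4.4.8.1 class events between consent and first treatment as baseline signs and symptoms.
- **A TEAE** needs onset on or after initiation of trial product, or worsening of an event already present (General Definitions, TEAE).
- **Periods** are defined in SAP 4.3.4. The MVA Vaccination Period takes "All AEs starting on the day of first MVA-BN-CV301 vaccination until the day prior to the first FPV-CV301", and an AE dated on a vaccination day goes to that vaccination's period. SAP 4.4.8.1 tabulates AEs by these periods.

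**The concern.** An AE that began and ended between consent and the first dose cannot be treatment-emergent. If its end date is recorded and its start date is not, the end date alone settles the matter. The table row for a wholly missing date ignores that information and assigns onset to the day of first treatment. The event then leaves the baseline signs and symptoms and enters the TEAE tables, with a start later than its own end.

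The trial is single-arm and its cohorts are small, so TEAE incidence is read directly with no control arm in which the same artefact would appear. Misclassified pre-treatment events therefore add to the apparent toxicity of the combination.

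A lesser matter is that SAP 4.3.4 has a second boundary, the first FPV-CV301 dose. SAP 4.3.2 says nothing about partial dates around it.

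**Working it through.** The plan states no figure on this point, so there is none to reproduce. The rules are applied literally to illustrative dates.

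**1. Wholly missing start, known end before dosing.** First dose 20 March 2019; AE ended 12 March 2019; start unknown.

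- Imputed start (4.3.2, missing-year row) = 20 March.
- The correction is not reached, because 20 March is not before the first vaccination.
- TEAE test: onset on or after first product; 20 March meets it, so the AE is treatment-emergent.
- Period (4.3.4): MVA Vaccination Period.
- Duration (4.3.5) = end − start + 1 = 12 − 20 + 1 = −7 days.

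In general, any end date E before the first dose D gives a duration of E − D + 1, which is zero or negative. The 4.3.2 footnote does not help: it only limits dates to the first and last visits.

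**2. Same AE, start known only as March 2019.** The table gives 1 March, which is before 20 March, so the correction's trigger is met. Its second condition has two readings.

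- *Start date alone:* March includes 20 March, so onset from then on is possible. The start becomes 20 March, the AE is a TEAE and the duration is −7 days.
- *Start and end together:* onset from 20 March is impossible for an event that ended on 12 March. The start stays before dosing and the AE stays pre-treatment.

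A missing month (1 January 2019) leads to the same two readings.

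**3. Size per event.** AE incidence is subjects with the event divided by subjects in the cohort (4.4.8.1). One subject is 1/33 = 3.0 or 1/35 = 2.9 percentage points in a full cohort. It is 1/14 = 7.1 or 1/13 = 7.7 points if the cohort stops at Stage 1. These are maxima: nothing changes for a subject who already counts for that event.

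**4. The first FPV-CV301 dose.** It is planned for Day 43 (protocol synopsis), with a permitted window of Days 39 to 47 (SAP Table 1).

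- The dose is at least 39 − 1 = 38 days after Day 1, which is longer than any month. The two never share a calendar month.
- The first of the FPV month is at earliest Day 43 − 30 = 13, or Day 39 − 30 = 9 at the edge of the window. It is always after Day 1, so the correction never applies. Over four years of Day 1 dates and all nine window days (1,461 × 9 = 13,149 combinations) it was triggered 0 times.
- Example: Day 1 on 4 March 2019, first FPV-CV301 on 15 April, AE dated April 2019. The imputed start is 1 April, trial Day 29, in the MVA period.
- Exception: a dose given on the 1st (3.3% of cases) is assigned to FPV by the same-day rule. The other 96.7% go to MVA.

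Now assume onset and dose day d uniform over a 30-day month:

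- truly FPV-period: Σ(31 − d)/900 = 465/900 = 51.7%;
- misassigned now: (465 − 30)/900 = 435/900 = 48.3%;
- misassigned if all such starts moved to the FPV date: Σ(d − 1)/900 = 435/900 = 48.3%.

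Real calendar months give 48.4% before and after.

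**The case against.** **The main point.** A careful programmer could treat a pre-dose end date as making later onset impossible, and so leave the start before dosing. That stands for a missing day or month, where the result depends on the reading. It does not help a wholly missing start, because that row has no condition to interpret. SAP 4.3.5 leaves duration missing when the start is missing. If that covers imputed starts, the negative duration disappears, but the TEAE classification remains. Imputed dates are flagged, so affected events can be found, but a flag does not reclassify them.

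**The FPV-CV301 boundary.** Three stronger readings are tempting, and the documents do not support them.

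- *The rule is called conservative but is anti-conservative for the boost vaccine.* In 4.3.2 the word refers to Day 1 only. The SAP makes no such claim for MVA against FPV.
- *Boost toxicity is under-counted.* This can hold only in the by-period split. Relationship is collected separately for each product, events related to FPV-CV301 have their own table category, and that category is also shown for the overall treatment period.
- *An AE with missing causality escapes attribution to FPV-CV301.* The general definition of a related TEAE does carry a date condition ("If a relationship is missing and the TEAE started after the initiation of an individual trial product"). SAP 4.4.8.1, however, counts any missing relationship as related, whatever the date. The two statements should be aligned, but the inference does not follow.

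**Conclusion.** The point holds, and it is small. For a wholly missing start date with a known end before the first dose, SAP 4.3.2 gives a result that contradicts the SAP's own definitions of a TEAE and of baseline signs and symptoms. This needs no assumption beyond such a record existing. For a missing day or month, the same error depends on judging what is possible from the start date alone, which the text allows but does not require. Each affected AE adds at most 2.9 to 3.0 percentage points to a full cohort's incidence. The documents give no expected number of incomplete dates, so no total can be stated.

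The absent convention at the first FPV-CV301 dose is real but secondary. It moves AEs between the MVA and FPV tables and leaves overall TEAE counts and investigator attribution unchanged. Under uniform onset about 48% of AEs dated only to that month are misassigned with or without a new rule, so adding one is a choice of direction and not a gain in accuracy.

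**What to change.** Keep the current rules and add to SAP 4.3.2:

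> An imputed AE start date may not be later than a known (complete or partial) AE end date. An AE whose known end date is before the first dose of trial product remains a pre-treatment AE (baseline sign or symptom), including when the start date is wholly missing.

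For a partial end date, the second sentence should apply only when the latest date it allows is before the first dose. The SAP should also say what start is stored in these cases. Leaving it missing is enough, since 4.3.5 then leaves the duration missing.

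Optionally, for an AE whose start is known only to the month of the first FPV-CV301 dose, set the start to that dose date when three things hold: the imputed date falls before it, the partial date allows onset on or after it, and no known end date precedes it. This matches the same-day convention in 4.3.4. The cost is that some AEs that truly began in the MVA period would be tabulated under FPV.

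The main change costs an addition of two sentences and one programming check, best made before database lock. It gives up nothing, because it affects only events whose recorded end date already rules out onset after dosing.

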4.3.3 Data Handling Conventions for Efficacy Analyses

Subjects who have no record of CR/PR and withdraw early from the trial or are lost to follow up will be considered as non-responders for the ORR analyses.

For PFS, if a subject has no date of death and has not progressed by the time of the analysis, the subject will be censored at the last radiologic assessment showing no progression has occurred. For sensitivity analyses on the FAS, if a subject has no post-baseline radiologic assessment, they will be censored on Day 1.

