#### **8.2.5.1 Progression of Underlying Malignancy**

For the purpose of this trial, progression of underlying malignancy is not considered an (S)AE. Hospitalization, prolonged hospitalization, or death due solely to the progression of underlying malignancy will be captured on the AE-section of the eCRF, but may NOT be reported as an

SAE. However, clinical symptoms of progression should be reported as (S)AEs if they cannot be determined to be exclusively due to the progression.

Symptomatic deterioration may occur in the absence of radiographic evidence of tumor progression in some subjects. Alternatively, the disease progression may be so evident that the investigator may elect not to perform further assessments. In such cases, the determination of clinical progression is based on symptomatic deterioration. In these cases, efforts should be made to quantitatively document the progression of the underlying malignancy to the extent possible.

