4.2 Analysis Populations

For the purpose of statistical analysis, there will be 2 analysis populations: Full Analysis Set (FAS) and the Efficacy Evaluable (EE) Set.

The FAS consists of all subjects taking any amount of trial vaccine, whether MVA-BN-CV301 or FPV-CV301. The FAS will be the primary population for all analyses.

The EE Set consists of all subjects from the FAS who meet the following criteria:

- Received 2 prime doses of MVA-BN-CV301 (Weeks 1 and 4)
- Have a baseline CT/MRI scan assessable per RECIST v1.1

The EE set will be used for sensitivity analyses of the primary and secondary efficacy endpoints.

Although the primary efficacy analysis is on the FAS population, enrollment may continue for Stage 1 until the EE set reaches the full sample size of 14 for Cohort 1, or 13 for Cohort 2 ([Section 2.6.4](#)).

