4.4.5.2 Secondary Endpoints

4.4.5.2.1 Progression-Free Survival

PFS is defined as the time interval from first treatment to objective tumor progression or death. Accordingly, the precise definition of progression and the timing of CT scans to document progression are very important. Every effort must be made to assure that timeframes for post-treatment CT scans are achieved, so that both treatment groups can be usefully compared.

Assessments must be adequate to evaluate target lesions, non-target lesions, and to search for new lesions.

The secondary endpoint of PFS will be based on the investigator's assessment using RECIST v1.1 response guidelines. PFS will be defined as the time from the day of first treatment to the start of disease progression or death (any cause), whichever occurs first. Subjects who do not have disease progression or have not died will be censored at the date when the last tumor assessment determines a lack of progression. If a subject begins a new anti-cancer therapy or has radiotherapy or surgery at a lesion site prior to documented progression (or death), the subject will be censored at the last assessment where the subject was documented as progression free prior to the intervention.

The Kaplan-Meier curve for PFS and the median PFS will be presented for the FAS.

Additionally, an investigator assessed PFS analysis that includes both investigator-judged PD according to RECIST v1.1 and symptomatic deterioration will be provided.

A binary endpoint for PFS will also be analyzed at milestone time points. The number and percentage of subjects who are progression free based on the above definition at 6, 9, 12, 18, and 24 months will be summarized within the FAS. The two-sided 90% exact binomial confidence interval for the PFS at each time point will be calculated using the Clopper-Pearson method.

A recently published meta-analysis concluded that in checkpoint inhibitor trials 6-month PFS rate is recommended as an endpoint because it is the best predictor of 12-month OS rate. In the absence of prospective validation, the decision adopted is to retain 6-month PFS rate as a secondary endpoint with the aim of complement the primary endpoint ORR in the interpretation of trial results as a whole.

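### The SAP's Day 1 censoring rule for FAS sensitivity analyses of PFS makes no exception for death or symptomatic deterioration, and the SAP does not say which analyses it covers

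*SAP*

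**What the plan says.** SAP 4.3.3 has two consecutive sentences on PFS censoring. The first opens "For PFS, if a subject has no date of death and has not progressed by the time of the analysis" and censors such a subject at the last scan without progression. The second reads "For sensitivity analyses on the FAS, if a subject has no post-baseline radiologic assessment, they will be censored on Day 1." It has its own condition, no post-baseline scan, and neither repeats nor withdraws the condition about death.

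SAP 4.4.5.2.1 defines PFS as the "time from the day of first treatment to the start of disease progression or death (any cause), whichever occurs first". Its censoring sentence is loosely joined ("Subjects who do not have disease progression or have not died will be censored at the date when the last tumor assessment" showed no progression), but read with the definition it means subjects with neither event. That section has no Day 1 rule, and neither does Protocol 9.7.2.1. It adds: "The Kaplan-Meier curve for PFS and the median PFS will be presented for the FAS." It also promises a further PFS analysis that counts symptomatic deterioration as well as RECIST progression, and binary progression-free proportions at 6, 9, 12, 18 and 24 months within the FAS.

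SAP 4.2 says "The FAS will be the primary population for all analyses" and gives the sensitivity role to the EE Set. The first post-baseline scan is at about Week 10 (SAP 2.6.4.1), planned Day 64.

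**The concern.** A subject who dies before any post-baseline scan meets two rules at once: the PFS definition, which makes the death an event, and the Day 1 sentence, which censors the subject. The SAP does not say which prevails.

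Symptomatic deterioration raises the same problem. Protocol 8.2.5.1 recognises that "the disease progression may be so evident that the investigator may elect not to perform further assessments". A subject who deteriorates before Week 10 and is never scanned is a case the supplementary PFS analysis exists to count, yet the Day 1 sentence, applied to that analysis, would remove it.

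Subjects censored on Day 1 leave the risk set before any event and contribute nothing to the curve. Those removed would be the earliest failures, so the curve and median can only move in the favourable direction.

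The label adds to the difficulty. No PFS analysis is called a sensitivity analysis on the FAS. The symptomatic-deterioration and iRECIST analyses are the natural candidates, but the reader has to guess.

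**Working it through.** **No figure to reproduce.** The documents give no PFS event count, PFS power or early-death rate. The two-stage ORR design figures are not touched by this point.

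**1. Subjects who could be involved.** Inputs:
- first scan on planned Day 64, so 63 days, or 63/30.4375 = 2.07 months, after first treatment;
- full cohort sizes of 33 and 35 (SAP 2.6.4.1);
- survival with atezolizumab quoted in Protocol 2.1: first-line cisplatin-ineligible, median 15.9 months and 75% alive at 12 months; second-line, medians of 11.4 and 8.6 months.

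Assuming exponential survival, the share dying before Day 64 is 1 − 0.5^(2.07/median), or 1 − 0.75^(2.07/12) from the landmark rate.

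| Cohort | Survival input | Share dying before Day 64 | Expected number |
|---|---|---|---|
| 1 | 75% at 12 months | 4.8% | 1.6 of 33 |
| 1 | median 15.9 months | 8.6% | 2.9 of 33 |
| 2 | median 11.4 months | 11.8% | 4.1 of 35 |
| 2 | median 8.6 months | 15.4% | 5.4 of 35 |

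Moving the scan within its 4-day window (Day 60 to 68) changes each number by about 0.3 at most. These are upper figures. The 12-week life-expectancy criterion (84 days) reaches past Day 64, and Protocol 4.2.5.1 allows a CT ahead of schedule for clinical reasons, so some early deaths would have a scan.

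**2. Effect on a Kaplan-Meier curve if the sentence were applied literally.** With e early deaths censored on Day 1 and k of n subjects progression-free at a given time, with no other censoring by then, the estimate moves from k/n to k/(n − e). For example, 13/33 = 39.4% becomes 13/30 = 43.3% with e = 3, and 14/35 = 40.0% becomes 14/30 = 46.7% with e = 5.

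A simulation gives the effect on the median: 3,000 cohorts per setting, exponential death and progression times, and progression seen at the next protocol scan. The documents give no atezolizumab PFS median. The value of 4.66 months is assumed from the 16.8% 12-month PFS quoted for second-line pembrolizumab: 12 × ln 2 / −ln 0.168 = 4.66. The shorter values of 2.7 and 2.1 months are assumptions too.

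| Cohort | OS median (months) | Assumed PFS median (months) | Median PFS day: deaths counted → censored on Day 1 | Kaplan-Meier estimate at Day 183 |
|---|---|---|---|---|
| 1 | 15.9 | 4.66 | 167 → 183 | 46% → 50% |
| 2 | 11.4 | 4.66 | 166 → 189 | 46% → 52% |
| 2 | 8.6 | 4.66 | 161 → 192 | 44% → 52% |
| 1 | 15.9 | 2.7 | 125 → 136 | 28% → 30% |
| 2 | 8.6 | 2.1 | 89 → 116 | 19% → 22% |

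**3. Which outputs can move.**
- Main FAS curve and median: SAP 4.4.5.2.1 counts the deaths and has no Day 1 rule, so none are removed.
- Milestone PFS: this is a proportion of the FAS. A subject who died is not progression-free, and Day 1 censoring adds nothing to the numerator. No text removes the subject from the denominator.
- ORR and OS: not governed by the sentence.
- FAS sensitivity or supplementary PFS curves and medians: exposed.

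**The case against.** The strongest reply is that the sentence should not be read alone. The one before it limits PFS censoring to subjects with no death and no progression, and sends them to their last scan. That leaves one gap, the event-free subject who never had a scan, and the Day 1 sentence fills it. On that reading SAP 4.3.3 and 4.4.5.2.1 agree. This is a sensible reading and may be the intended one, but the text does not state it, and making it explicit needs the same edit.

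The second reply is the sentence's own limit to sensitivity analyses. It stands. A reader might infer that early deaths vanish from the PFS analysis generally; the documents do not support that, because the main analysis counts them. The limit is not a full answer, since no such analysis is identified and this is the only explicit instruction for subjects without a post-baseline scan. A programmer could carry it into the main analysis, though that is a risk and not something the SAP says.

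The third reply also stands. A reader might take the Kaplan-Meier shifts above as inflation of the planned 6-month PFS rate. That rate is a binary FAS proportion, so they do not describe it.

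Finally, it can be said that sensitivity analyses may be run on a primary population. That is true. The fault is that they are not named, not that the FAS has been relabelled.

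**Conclusion.** The point holds as an unqualified rule that needs one clause. Applied as written, it would censor at time zero deaths before the first scan, contrary to the PFS definition, and would remove scan-free symptomatic deterioration from the analysis designed to include it. It is not a demonstrated contradiction in the main PFS analysis, and no bias in the milestone PFS rates, ORR or OS is shown.

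The number who could be involved is about 2 to 3 of 33 in Cohort 1 and 4 to 5 of 35 in Cohort 2. This assumes exponential survival at rates from other trials quoted in the protocol, and would be lower if the life-expectancy criterion works. In the simulated settings the median of an affected analysis lengthens by about 11 to 31 days; those values also rest on assumed PFS medians. The direction does not depend on the assumptions.

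PFS is a secondary endpoint with no hypothesis test, so no trial decision rests on this. It should still be settled before PFS is programmed.

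**What to change.** Replace the Day 1 sentence in SAP 4.3.3 with:

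> In all FAS analyses of PFS, a subject with no post-baseline radiologic assessment and no PFS event under the definition used in that analysis (death, progression or, where included, symptomatic deterioration) is censored on Day 1, including subjects lost to follow-up; a death before any scan is an event at the date of death, subject to the censoring for new anti-cancer therapy, radiotherapy or surgery at a lesion site in Section 4.4.5.2.1.

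This removes the limit to sensitivity analyses on the FAS. If the sponsor prefers to keep that limit, the SAP should name the analyses meant and state separately the rule for event-free subjects without a scan in the main analysis. The last clause is needed because an unqualified rule that every death is an event would override the existing censoring for intervening cancer treatment.

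The cost is one SAP sentence. Data collection, sample size and the ORR decision rules do not change. Any analysis that would have used the literal rule becomes slightly less favourable.
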